		Table 5 (Covariates)	Added explicit exposure assessment window definitions consistent with proprietary vendor rules	To ensure consistent exposure classification across databases
		Table 5 (Covariates)	Removed covariate dem_age_initial_diagnosis (Age at initial diagnosis)	Age at index date is already adjusted for; age at initial diagnosis adds redundancy without improving confounding control
		Table 5 (Covariates)	Removed covariate dem_sex (Sex)	Breast cancer trial population consists exclusively of women; adjustment for sex is unnecessary
		6.6.7 Context and rationale for covariates	Clarified rationale for excluding sex and age at initial diagnosis as covariates	To document alignment between clinical trial population, data structure, and analytic adjustment strategy
		6. Research methods / biomarker definitions	Introduced new function edbx_get_her2() implementing an algorithm based on ASCO HER2 testing guidelines	To improve accuracy and standardization of HER2 status classification across EHR data sources
February 9, 2026	V2.0	6.1.1, Table 7, Table 8 (Sensitivity analyses), 10.3 (Power)	EDB4 was excluded from the primary analysis and included in sensitivity analysis #11 (meta-analysis)	Because the study identification period (10/01/2018-09/30/2023) began after the 2017 approval of ribociclib, patients who initiated ribociclib before 10/01/2018 were only included if they survived until the start of the study period, which may introduce immortal time and selection bias due to left truncation.

4. Rationale and background

Randomized controlled trials (RCTs) are generally regarded as the gold-standard of evidence for establishing efficacy of medical products. However, real-world data (RWD) are increasingly used to complement evidence from RCTs. Yet, to have confidence in the accuracy of treatment efficacy estimates from RWD, investigators need to know what questions can be validly answered, with which non-interventional study designs, and which analysis methods are appropriate, given the data that is available. Building on a process from the RCT DUPLICATE initiative,¹⁻⁴ **Emulation of Comparative Oncology trials with Real-world Evidence (ENCORE)** is part of the expansion project specific to oncology and aims to emulate 12 randomized oncology RCTs using multiple EHR data sources.

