Eligibility criteria	
 • Women aged ≥ 18 years with diagnosis of breast cancer • Histologically or cytologically confirmed adenocarcinoma of the breast • Locoregionally recurrent or metastatic disease not amenable to curative resection/radiotherapy • ER-positive status • HER2-negative status • Postmenopausal status • No prior systemic therapy for advanced/metastatic ER+ disease • Measurable disease per RECIST v1.1 or bone-only disease confirmed by imaging • WHO/ECOG performance status 0 or 1 	
 • Female aged ≥ 18 years at treatment initiation with a diagnosis of breast cancer • Diagnosis of breast adenocarcinoma via histology/pathology records • Evidence of metastatic or recurrent disease • Documentation of ER-positive (or -missing) status • Documentation of HER2-negative (or -missing) status • N/A • No systemic anti-cancer therapy* following initial record indicating metastatic disease and prior to index date • N/A • WHO/ECOG performance status of 0 or 1 within 90 days of index date 	
 • If ER is missing and a patient received the exposures of interest, then ER is likely to be positive given the alignment with the indication for the exposures of interest • If HER2 is missing and a patient received the exposures of interest, then HER2 is likely to be negative given the alignment with the indication for the exposures of interest • Although not directly captured in RWD, it is likely to be fulfilled given the alignment with the indication for the exposures of interest • It is reasonable to assume that all patients in RWD had evidence of disease if they received treatment; additionally OS primary endpoint does not require measurable disease

- No symptomatic, life-threatening visceral disease (e.g., massive effusions, >50% liver involvement)

- N/A

- No active or symptomatic CNS metastases

- Record of CNS metastases prior to or on index date

- No prior treatment with CDK4/6 inhibitors

- Exclude patients with prior CDK4/6 inhibitor exposure

- No recurrence during or within 12 months of adjuvant non-steroidal AI (anastrozole or letrozole)

- Treatment with letrozole or anastrozole ≤ 12 Months prior to date of metastatic diagnosis

- No other malignancy within 3 years

- No prior record of non-breast malignancy within 3 years

- N/A

- Restriction to the time period 2015-2022

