6.6.7. Context and rationale for covariates

We identified a series of covariates that are strong prognostic factors for the outcome and auxiliary covariates which may be useful to impute missing data. Such covariates comprise demographics, covariates indicating disease-severity, cancer-specific covariates as well as pathological and genetic factors. In addition, selected labs and vitals are considered since they were shown to carry a high amount of prognostic information as described in Becker, Weberpals, et al.¹¹ For these variables, additional plausibility checks and transformations are carried out. In detail, labs and vitals are individually checked if they cross a certain biologically implausible threshold (e.g., a heart rate of 0) in which cases the values are set missing and imputed in a next step. These thresholds were compiled by experienced practicing physicians and medical oncologists and are listed in appendix **Table 8** and **Table 9**.

Note that not all covariates are available across all databases used for this trial emulation. In the analytical stage, the most comprehensive model will be fit for each database individually.

Table 5. Operational definitions of key covariates used for trial emulation.

Characteristic	Harmonized analysis variable name	R function to derive covariate (see pdf in appendix)	Details ¹	Variable encoding	Assessment window
Age at index date	dem_age_index	edbx_get_demographics()	Age measured at index date	Binary (<60, 65+); modelled continuously in ROPRO ¹⁰	[0;0]
Year of index date	c_year_index	De novo derived from dt_index	Calendar year in which patient initiated study treatment	Nominal (<2020, 2020+)	[0;0]
Family history	dem_family_history	edbx_get_demographics()	Family history of cancer. Not available in EDB1.	Logical (TRUE, FALSE)	[0;0] (no specific date is associated)
Race	dem_race	edbx_get_demographics()	Race categorized as in the original RCT	Binary (Asian vs non-Asian)	[0;0]
Ethnicity	dem_ethnicity	edbx_get_demographics()	Ethnicity	Hispanic, Non-Hispanic	[0;0]
Region	dem_region	edbx_get_demographics()	US region patient receives care in; if given on a state level, region is manually mapped (see Table 10)	Nominal (Northeast, South, West, Midwest)	[0;0]
Practice type	dem_practice	edbx_get_demographics()	Setting patient is receiving care at. Not available in EDB3 and EDB4.	Nominal (academic, community, academic & community)	[-inf;0]

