Socio-economic status	dem_ses	edbx_get_demographics()	Socioeconomic status (SES) index based on residence area of patient. Not available in EDB3 and EDB4.	Nominal (from '1 - Lowest SES' through '5 - Highest SES')	[-inf;0]
Smoking	c_smoking_history	edbx_get_demographics()	History of current or former (= TRUE) or never (= FALSE) smoking on or anytime before index date; if there are multiple records per patient, any evidence of former/current smoking is prioritized. IN EDB1, "smoking history" is not available for breast cancer.	Binary logical (TRUE, FALSE)	[-inf;0]
ECOG	c_ecog	edbx_get_ecog()	ECOG performance status measured closest to index date within assessment window. In	Nominal (0, 1, 2, 3, 4); modelled as ordinal numeric in ROPRO ¹⁰ ; due to I/E	[-90;0]

Characteristic	Harmonized analysis variable name	R function to derive covariate (see pdf in appendix)	Details ¹	Variable encoding	Assessment window
			case of ties, the lower ECOG value is selected	criteria ECOG is modelled as a binary (0, 1) covariate	
Stage	c_stage_initial_dx	edbx_get_diagnosis_solid()	AJCC summary group stage at initial diagnosis	Ordinal numeric (from 0 to IV with sub-categories, e.g., IA1) ¹⁰	[-inf;0] at initial diagnosis of primary cancer
De novo metastatic status	c_de_novo_mets_dx	edbx_get_diagnosis_solid()	Evidence of presence of one or multiple metastases at/before initial diagnosis	Binary logical (TRUE, FALSE)	[-inf;0] at initial diagnosis of primary cancer
Number of metastatic sites	c_number_met_sites	edbx_get_diagnosis_solid()/edbx_get_number_met_sites_solid()	Number of metastatic sites for a given patient before/on index date	Integer	[-inf;X]; Proprietary business-rule-based covariate assessment window
Time between initial diagnosis to index date	c_time_dx_to_index	edbx_get_diagnosis_solid()	Time in days between initial diagnosis to index date. Quartiles will be used because there may be “negative” times intervals due to date imprecision of the lines of therapy.	Categorical (quartiles)	[-initial dx;0]
Time between earliest evidence of a metastatic and index date	c_time_met_dx_to_index_quartiles	edbx_get_diagnosis_solid()	Time in days between earliest evidence of a metastatic diagnosis and index date. Quartiles will be used because there may be “negative” times intervals due to date imprecision of the lines of therapy.	Categorical (quartiles)	[met dx;0]

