A. Primary analysis

Table 7. Primary, secondary, and subgroup analysis specification

Hypothesis:	Initiation of palbociclib plus letrozole decreases the hazard of all-cause mortality as compared to initiation of letrozole alone
Exposure contrast:	Initiation of palbociclib plus letrozole vs letrozole alone
Primary outcome:	Time to all-cause mortality (OS)
Secondary outcome:	Time-to-next-treatment (TTNT) defined as a composite outcome of all-cause mortality or adding or switching to a next-line treatment. ^{35,36}
Databases used:	EDB1 and EDB3 (primary analysis), EDB4 (sensitivity analysis)
Time period:	From 2015 (approval year for palbociclib) - 2022 (publication of final OS outcome results for competitor ribociclib) ⁷
Analytic software:	R 4.3.2. Version control of code and R packages will be established through git and Posit package manager, respectively. All packages are frozen to their most recent version as of April 25, 2024.
Model(s): (provide details or code)	See example code here . The annotated code for the trial emulation will be hosted at https://drugapi.gitlab-pages.partners.org/encore/paloma2-nct-01740427/ (access only through MGB network for authorized personnel)
Confounding adjustment method	Name method and provide relevant details, e.g. bivariate, multivariable, propensity score matching (specify matching algorithm ratio and caliper), propensity score weighting (specify weight formula, trimming, truncation), propensity score stratification (specify strata definition), other.
	1:1 propensity score nearest neighbor matching without replacement and a caliper of 1% of propensity score standard deviation
Missing data methods	Name method and provide relevant details, e.g. missing indicators, complete case, last value carried forward, multiple imputation (specify model/variables), other.
	Multiple imputation by chained equations using a random forest imputation model across all covariate types. The number of imputed datasets will be determined by the average proportion of missing values across all partially observed covariates. Imputation models will include all variables of the substantive model, i.e., exposure, outcome, confounders/prognostic factors and additional auxiliary covariates.
Subgroup Analyses	List all subgroups

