Exclusion 1	HER2-positive breast cancer	$[-\infty; 0]$	Any HER2+ status prior to or on index date	Any HER2+ status prior to or on index date	Any HER2+ status prior to or on index date	If HER2 is missing and a patient received the exposures of interest, then HER2 is likely to be negative given the alignment with the indication for the exposures of interest	edbx_get_her2()
Exclusion 2	Patients with advanced, symptomatic, visceral spread, that are at risk of life-threatening complications in the short term (including patients with massive uncontrolled effusions [pleural, pericardial, peritoneal], pulmonary lymphangitis, and over 50% liver involvement).	NA	NA	NA	NA	This is a safety criterion for the trial and less relevant to real-world treatment setting, given that patients received treatments of interest	
Exclusion 3	Known active uncontrolled or symptomatic CNS metastases, carcinomatous meningitis, or leptomeningeal disease as indicated by clinical symptoms, cerebral edema, and/or progressive growth. Patients with a history of CNS metastases or cord compression are eligible if they have been definitively treated with local therapy (eg, radiotherapy, stereotactic surgery) and are clinically stable off anticonvulsants and steroids for at least 4 weeks before randomization.	$[-\infty; 0]$	Record of CNS metastases prior to or on index date	Record of CNS metastases prior to or on index date	Record of CNS metastases prior to or on index date		edbx_get_diagnosis_solid()
Exclusion 4	Prior neoadjuvant or adjuvant treatment with a non-steroidal aromatase inhibitor (ie, anastrozole or letrozole) with disease recurrence while on or within 12 months of completing treatment.	[MBC-365; MBC-1]	Treatment with letrozole or anastrozole ≤ 12 months from MBC	Treatment with letrozole or anastrozole ≤ 12 months from MBC	Treatment with letrozole or anastrozole ≤ 12 months from MBC		
Exclusion 5	Prior treatment with any CDK4/6 inhibitor.	$[-\infty; -1]$	Prior treatment with ribociclib, palbociclib, abemaciclib	Prior treatment with ribociclib, palbociclib, abemaciclib	Prior treatment with ribociclib, palbociclib, abemaciclib		
Exclusion 6	Major surgery, chemotherapy, radiotherapy, any investigational agents, or other anti-cancer therapy within 2 weeks before randomization. Patients who received prior radiotherapy to 25% of bone marrow are not eligible independent of when it was received (see Appendix 4).	NA	NA	NA	NA		Proxied by 1st line therapy inclusion

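### Age is coded in two levels with no place for ages 60-64, and index year in two levels over eight years; the plan neither enters nor checks the uncollapsed values in the propensity score analysis.

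*Combined protocol and SAP*

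**What the plan says.** **Age.** Table 5 in section 6.6.7 gives the encoding of age at index date as "Binary (<60, 65+); modelled continuously in ROPRO". The amendment log (section 3) records that age at initial diagnosis was removed, on the ground that "Age at index date is already adjusted for; age at initial diagnosis adds redundancy without improving confounding control". Age at index is therefore the only age term left. The subgroup list in Table 7 splits age at 65 with no gap. The Excel appendix Table 2 (Inclusion 1) shows that age at index is held to the year.

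**Calendar year.** Table 5 encodes index year as "Nominal (<2020, 2020", the second level running to the end of the period. Table 2 sets the eligible period: "Restriction to the time period 2015-2022".

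**Adjustment.** The primary method in Table 7 is "1:1 propensity score nearest neighbor matching without replacement and a caliper of 1% of propensity score standard deviation". Section 6.7.1 then fits a Cox model in the matched set and names no further covariates. The Cox model depends on sufficient balance, judged by absolute standardized mean differences (ASMDs), with no numerical threshold stated for the matching step. Section 10.2 describes the balance figures as covering covariates in the propensity score models.

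**Sensitivity analyses.** Of the twelve in section 6.7.1, only #1 brings in continuous age, through matching on the ROPRO score, and the plan labels that analysis experimental.

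**The concern.** Two problems sit in the same line of Table 5.

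The first is a plain specification error. Read literally, patients aged 60-64 belong to neither age level. The text does not say whether they would be dropped, imputed or assigned to one side. The lower limit may be a slip for 65, but the plan has to say so.

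The second remains after that correction. Matching on a propensity score that contains a two-level variable aims to balance the shares in the two levels. It does not aim to balance the values inside each level. If one arm is younger overall, it will usually be younger within each level too. The same applies to index year, where eight calendar years become two bins. An ASMD computed on the collapsed variable can be zero while the underlying variable still differs.

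The study is meant to judge concordance with a near-null trial result (overall survival HR 0.96). A residual shift of a few percent in the HR is of the same order as that benchmark effect, and it would not shrink with more data.

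**Working it through.** **1. The plan's own figure.** Section 10.3 gives power for HR 0.92 with 1021 events (EDB1) and 331 events (EDB3). By Schoenfeld, two-sided 5%, 1:1, with ln 0.92 = -0.0834:

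- EDB1: Φ(√1021/2 × 0.0834 − 1.96) = Φ(−0.63) = 0.265 (stated 0.27).
- EDB3: Φ(√331/2 × 0.0834 − 1.96) = Φ(−1.20) = 0.115 (stated 0.11).

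Both reproduce. Pooled events are 1021 + 331 = 1352, so SE(log HR) ≈ 2/√1352 = 0.054. The 95% interval then spans a factor of about exp(1.96 × 0.054) = 1.11 each way. This is the yardstick for the shifts below.

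**2. Inputs for age.** The text gives no age distribution by arm, so all of these are assumptions: normal ages truncated to 25-95, SD 11, palbociclib mean 64, letrozole mean 70 (6-year gap) or 68 (4-year gap), and a mortality HR per decade of 1.2, 1.3 or 1.5. The cut is taken as corrected to 65 and balanced exactly. Palbociclib is reweighted to the letrozole shares, because section 6.7.1 expects the estimand to lie nearer the effect in the controls.

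**3. Ages 60-64.** With means 70 and 64, about 14% of the letrozole arm and 18% of the palbociclib arm fall in the uncoded band.

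**4. Residual age gap.** Residual = w × (difference in mean age below 65) + (1 − w) × (difference at 65 and over), where w is the letrozole share below 65. Differences are palbociclib minus letrozole.

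| Raw gap | w | Below 65 | 65 and over | Residual | ASMD (residual/11) |
|---|---|---|---|---|---|
| 6 years | 0.33 | 55.9 − 57.8 = −1.95 | 73.3 − 75.5 = −2.17 | 0.33(−1.95) + 0.67(−2.17) = −2.1 | 0.19 |
| 4 years | 0.40 | 55.9 − 57.2 = −1.37 | 73.3 − 74.7 = −1.39 | 0.40(−1.37) + 0.60(−1.39) = −1.4 | 0.13 |

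The differences were computed before the means were rounded. A little over a third of the raw gap survives exact balance on the binary.

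**5. Effect on the HR.** Factor = exp(residual/10 × ln HR per decade).

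| Raw gap | 1.2 per decade | 1.3 | 1.5 |
|---|---|---|---|
| 6 years | 0.96 | 0.95 | 0.92 |
| 4 years | 0.98 | 0.96 | 0.95 |

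With wider inputs (ages centred on 65, SD 10-12, gaps of 2 to 8 years, HR per decade 1.1 to 1.5) the factor runs from 0.99 to 0.89.

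**6. Calendar year.** The initiation trends in Figures 11-13 are not in the text, so uptake is also assumed: equal initiations per year, and a palbociclib share rising over 2015-2022 from 43% to 75% at the flattest or from 27% to 96% at the steepest. After exact balance on the two bins, 0.3 to 1.0 year of gap remains (32% to 41% of the raw gap; ASMD 0.15 to 0.54). With a mortality HR per later calendar year of 0.99 to 0.95, the factor is 0.99^0.33 = 0.997 to 0.95^1.03 = 0.95.

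**The case against.** The best reply has four parts.

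- **The propensity model is not listed term by term.** Table 5 mixes confounders with imputation auxiliaries, and section 6.6.7 says only that the fullest model will be fitted in each database. Binary age in the model is the natural reading, since the one continuous use stated is ROPRO, but it is not stated outright. This stands as a caution, and it is also a reason to state the form.
- **Other covariates absorb part of the gap.** Performance status, stage, time since diagnosis and many continuous labs and vitals are in the covariate set. This stands: the factors above treat age, or year, in isolation.
- **The shift is inside the sampling error.** A change of 2% to 8% is smaller than the pooled half-width of about 11%. This also stands, although bias and sampling error are different things, and only the latter falls with sample size.
- **Sensitivity #1 uses continuous age.** This is true, but it changes the whole matching score, is labelled experimental, and does not show what finer coding does to the primary estimate.

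A reader might also infer that the balance figures cannot reveal the problem. Figures 7-9 are not available in the text, and nothing says whether age is plotted as binary or in years. The supportable statement is that the text does not specify a check on the uncollapsed values. Nor do the residual ASMDs above breach a rule of the plan: the 0.1 cut-off appears only in the missing-data diagnostics, by analogy.

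**Conclusion.** The age categories are wrong as written: ages 60-64 are unplaced and Tables 5 and 7 disagree. The coarse coding of age and index year is an avoidable weakness in the primary adjustment. Under the stated assumptions the age coding alone would leave 1.4 to 2.1 years of imbalance and multiply the HR by about 0.98 to 0.92, before any absorption by correlated covariates. The documents do not allow the actual size to be computed. This should be fixed, but it does not by itself undermine the study.

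Three stronger readings are not supported.

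- **Strong confounding in the primary HR, favouring palbociclib.** The age and uptake differences between arms and the prognostic slopes are all assumed here. Other factors, such as disease burden, could act in the opposite direction, so no net direction follows.
- **Coarse coding of metastatic disease.** The variable is "Number of metastatic sites for a given patient before/on index date", stored as an integer. The type of site is absent from Table 5, but that is a separate question. A criterion based on "Record of CNS metastases prior to or on index date" does not establish that usable visceral or bone-only indicators exist.
- **Race.** "Binary (Asian vs non-Asian" follows the trial's coding by stated intent, and no effect of recoding it has been shown.

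**What to change.** 1. In Table 5, correct the age categories to <65 and ≥65, matching Table 7, and use them for tables and subgroups only.
2. In the propensity model, enter age in years (spline, or linear plus quadratic) and index year as single years. State this in section 6.7.1 or Table 7.
3. Report ASMDs for age in years and for single index year, before and after matching, across the imputed datasets.

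The cost is a change of wording and a model formula. Age to the year is already held, and index year comes from the index date. Matching would have to be rerun and the matched numbers and events in section 10.3 updated. The one downside is possibly a few lost matches under the narrow caliper.

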6.7. Data analysis

6.7.1. Context and rationale for analysis plan

To emulate the PALOMA-2 trial, the following analytical workflow will be used (Figure 2). First, an analytical cohort with covariates on key eligibility criteria and prognostic factors will be derived across all databases. To ensure reproducibility and consistency throughout the entire ENCORE project, the internally developed *encore.io* R package streamlines this process using the functions referenced in Table 5. Operational definitions of key covariates used for trial emulation. Table 5 (code documentation see appendix).¹⁶ The analytical cohort will be derived by first identifying a metastatic breast cancer inception cohort of initiators of palbociclib plus letrozole or letrozole alone in the first-line setting as described in section 6.6.4. Next, key eligibility criteria will be applied in which patients with missing values are considered eligible in the respective attrition steps to allow thorough missing data investigations.

Figure 2. Illustration of principled analytical workflow.

Once a full analytic cohort is built, principled missing data investigations will be employed to empirically assess assumptions on potentially underlying missingness mechanisms according to Rubin's classification of missing data (i.e., missing completely at random [MCAR], missing at random [MAR] and missing not at random [MNAR]).¹⁷ To that end, we will adopt a principled process on missing data that was developed as part of a FDA Sentinel Innovation Center causal inference workstream that empirically evaluates different aspects across partially observed covariates based on three group diagnostics (Table 6).^{18,19} In brief, the first group diagnostics computes distributions and absolute standardized mean differences (ASMD) between patients with and without an observed value for a given partially observed covariates. If missingness can be explained by observed covariates such as in MAR mechanisms, patient characteristics will significantly differ which will (in analogy to propensity scores) be indicated by ASMDs > 0.1. In addition, Hotelling's²⁰ and Little's²¹ tests additionally provide formal hypothesis tests for such comparisons in which high test statistics and a rejection of the null hypothesis would provide evidence for differences in the distribution of patient characteristics and suggest the underlying mechanism is not MCAR or MNAR. Group 2 diagnostics assess the ability to predict missingness based on observed covariates by fitting a classification model to predict the missingness indicator of the partially observed covariate. To that end, we will fit a random forest (RF) classification model using observed covariates with a 70/30 train-test split of the complete cohort. A sufficiently high area under the receiver operating characteristic curve (AUC) metric of the test dataset may demonstrate that missingness can be predicted well and could point towards MAR as a likely mechanism as opposed to an AUC~0.5 which would suggest MCAR or MNAR. Group 3 diagnostics evaluates the association between the missingness indicator of the partially observed covariates and the outcome (OS). If the missingness of a confounder cannot be explained or approximated by observed covariates and a difference in the outcome is observed depending on the missingness indicator (e.g., $HR_{\text{missingness indicator}} \neq 1$), this may be indicative of an underlying MNAR mechanism. These empirical diagnostics will be implemented through the smdi R package²² and be further enhanced by clinical expert knowledge.

Table 6. Diagnostics to empirically differentiate and characterize missing data mechanisms.

Diagnostic metric	Group 1 Diagnostics		Group 2 Diagnostics	Group 3 Diagnostics
	Absolute standardized mean difference (ASMD)	P-value Hotelling ²⁰ Little ²¹	Area under the receiver operating curve (AUC)	Log HR (missingness indicator)
Purpose	Comparison of distributions between patients with vs. without observed value of the partially observed covariate.		Assessing the ability to predict missingness based on observed covariates.	Check whether missingness of a covariate is associated with the outcome (differential missingness).
Example value	ASMD = 0.1	p-value < 0.001	AUC = 0.5	log HR = 0.1 (0.05 to 0.2)
Interpretation	
<0.1^a: no imbalances in observed patient characteristics; missingness may be likely completely at random or not at random (~MCAR, ~MNAR).
 
>0.1^a: imbalances in observed patient characteristics; missingness may be likely at random (~MAR).
	High test statistics and low p-values indicate differences in baseline covariate distributions and null hypothesis would be rejected (~MAR).	
AUC values ~ 0.5 indicate completely random or not at random prediction (~MCAR, ~MNAR).
 
Values meaningfully above 0.5 indicate stronger relationships between covariates and missingness (~MAR).
	
No association in either univariate or adjusted model and no meaningful difference in the log HR after full adjustment (~MCAR).
 
Association in univariate but not fully adjusted model (~MAR).
 
Meaningful difference in the log HR also after full adjustment (~MNAR).

[figure not shown]
Abbreviations: ASMD = Median absolute standardized mean difference across all covariates, AUC = Area under the curve, CI = Confidence interval, MAR = Missing at random mechanism in which the missingness probability depends on observed covariates, MCAR = Missing completely at random mechanism in which each patients has the same missingness probability, MNAR(unmeasured) = Missing not at random mechanism in which the missingness can only be explained by a covariate which is not observed in the underlying dataset, MNAR(value) = Missing not at random mechanism in which the missingness just depends on the actual value of the partially observed confounder of interest itself.

^a Analogous to propensity score-based balance measures.²³

